### **6.8.2.5 Time to Achieve IGA Success**

Time to achieve IGA success will be summarized using the Kaplan-Meier method and displayed graphically. Medians, as well as 25% and 75% percentiles will be presented. Elapsed times will be computed from the date of first dose to the date of IGA assessment. Subjects not achieving the event by the time of completion/discontinuation will be right censored using the date of the last recorded non-missing assessment.

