### **5.1.2 Secondary Efficacy Endpoints**

The secondary efficacy endpoints for the study are:

- The change from Baseline in the total Signs of AD score at Day 85,
- The proportion of subjects with an IGA of Clear or Almost Clear at Day 85,
- The proportion of subjects with at least a 2-grade improvement in IGA from Baseline at Day 85,
- The change from Baseline in the percent of total body surface area (BSA) affected by AD at Day 85,
- The time to achieve IGA success, and
- The change from Baseline to Day 85 in the Itch-Numerical Rating Scale (I-NRS).

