## **7. DETERMINATION OF SAMPLE SIZE**

The sample size for this study is based on clinical considerations only. Subjects will be randomized 1:1 with 100 subjects in each treatment group for a total 200 subjects. This is considered adequate to evaluate the safety and tolerability and preliminary information on efficacy of twice daily BTX 1204 4% in the treatment of moderate atopic dermatitis in subjects aged 12 to 70 years of age.

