SOURCE: USERNAME\SPONSOR\PROJECT\JOBNAME (DATE,TIME)

Repeat Table 14.2.2.2.1 for the following:

Table 14.2.2.2.2: Secondary Endpoint: Dichotomized IGA at Day 85 (mITT Population)

Table 14.2.2.2.3: Secondary Endpoint: Dichotomized IGA at Day 85 (PP Population)

**Programming note:** *Replace last footnote with* - Note: No imputations were made for missing data.

Table 14.2.2.3.1: Secondary Endpoint: Change from Baseline in Percent of Total BSA Affected by AD at Day 85  
(ITT Population)

	BTX 1204 4% BID (N=xxx)	Vehicle BID (N=xxx)	Treatment P-Value
Change from Baseline in Total BSA Affected by AD			
n	xx	xx	
Mean	xx.x	xx.x	
SD	xx.xx	xx.xx	
Median	xx.x	xx.x	
Min., Max.	xx, xx	xx, xx	
LSMean a	xx.x		x.xxx a
LSSD a	xx.xx		

a Least squares mean, standard deviation, and p-value from an analysis of covariance with baseline Total BSA Affected by AD and treatment as covariates.

Note: Missing values imputed using LOCF.

SOURCE: USERNAME/SPONSOR/PROJECT/JOBNAME (DATE, TIME)

Repeat Table 14.2.2.3.1 for the following:

Table 14.2.2.3.2: Secondary Endpoint: Change from Baseline in Percent of Total BSA Affected by AD at Day 85 (mITT Population)

Table 14.2.2.3.3: Secondary Endpoint: Change from Baseline in Percent of Total BSA Affected by AD at Day 85 (PP Population)

**Programming note:** *Replace last footnote with* - Note: No imputations were made for missing data.

Table 14.2.2.4.1: Secondary Endpoint: Time to IGA Success  
(ITT Population)

	BTX 1204 4% BID (N=xxx)	Vehicle BID (N=xxx)
Subjects with a Non-Missing Post-Baseline IGA	xx	xx
Subjects with IGA Success a	xx ( xx.x%)	xx ( xx.x%)
Subjects Censored	xx ( xx.x%)	xx ( xx.x%)
Time to IGA Success a (Days)		
Minimum b	xx	xx
25 th Percentile c	xx.x	xx.x
50 th Percentile c	xx.x	xx.x
75 th Percentile c	xx.x	xx.x
Maximum b	xx	xx

a IGA Success is defined as an IGA score of Clear or Almost Clear with at least a 2-grade improvement from baseline.

b Observed time to event.

c Estimated using Kaplan-Meier methods.

Note: Elapsed times are computed from the date of first dose to the date of IGA assessment.

SOURCE: USERNAME\SPONSOR\PROJECT\JOBNAME (DATE,TIME)

**Programming note:** Minimum and Maximum values are among subjects achieving the event. Censored subjects are not considered.

Repeat Table 14.2.2.4.1 for the following:

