## 11. INDEX OF PLANNED FIGURES

Figure 14.2.1.5: Sensitivity Tipping-Point Analyses of the Primary Efficacy Endpoint: Dichotomized IGA Success at Day 85 (Intent-to-Treat Population) ..	103
Figure 14.2.2.4.4: Secondary Endpoint: Kaplan Meier Curves for Time to IGA Success (ITT Population) .....	104
Figure 14.2.2.4.5: Secondary Endpoint: Kaplan Meier Curves for Time to IGA Success (mITT Population) .....	105
Figure 14.2.2.4.6: Secondary Endpoint: Kaplan Meier Curves for Time to IGA Success (PP Population) .....	105

[figure not shown]
Figure 14.2.1.5: Sensitivity Tipping-Point Analyses of the Primary Efficacy Endpoint: Dichotomized IGA Success at Day 85 (Intent-to-Treat Population)

Note: The horizontal and vertical axes indicate the potential number of successes among subjects with missing data in each treatment group. Each plotted point indicates the number of imputed successes in each treatment group that results in a p-value greater than 0.05. The red lines represent the number of imputed successes from the primary analysis using last observation carried forward (LOCF) to impute missing values.

SOURCE: USERNAME/SPONSOR/PROJECT/JOBNAME (DATE,TIME)

Figure 14.2.2.4.4: Secondary Endpoint: Kaplan Meier Curves for Time to IGA Success (ITT Population)

Note: Circles represent censored observations.  
SOURCE: USERNAME/SPONSOR/PROJECT/JOBNAME (DATE,TIME)

Repeat Table 14.2.2.4.4 for the following:

Figure 14.2.2.4.5: Secondary Endpoint: Kaplan Meier Curves for Time to IGA Success (mITT Population)

Figure 14.2.2.4.6: Secondary Endpoint: Kaplan Meier Curves for Time to IGA Success (PP Population)

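### Time to IGA success has no effect estimate, confidence interval or formal between-arm comparison, and its tabulated percentiles may mostly go unreached

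*SAP*

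**What the plan says.** SAP 5.1.2 lists time to IGA success among the secondary efficacy endpoints. SAP 6.8.2.5 gives the method: "Time to achieve IGA success will be summarized using the Kaplan-Meier method and displayed graphically". It continues: "Medians, as well as 25% and 75% percentiles will be presented". On censoring it says: "Subjects not achieving the event by the time of completion/discontinuation will be right censored using the date of the last recorded non-missing assessment".

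The shell for Table 14.2.2.4.1 opens with the row "Subjects with a Non-Missing Post-Baseline IGA". By arm it then gives the number and percentage with success, the number and percentage censored, the observed minimum and maximum, and the three Kaplan-Meier percentiles. Unlike the shells for the primary endpoint and for Signs of AD, it has no p-value column. It also has no hazard ratio, confidence interval or cumulative success estimate at a fixed time. Kaplan-Meier curves are planned for the ITT, mITT and PP populations (SAP section 11).

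Protocol 9.3.3 names no method for this endpoint. On size, SAP section 7 says "Subjects will be randomized 1:1 with 100 subjects in each treatment group for a total 200 subjects" and "The sample size for this study is based on clinical considerations only". No success rate is given for either arm.

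**The concern.** Percentiles of a time-to-event curve are useful when most subjects have the event. Here the event is reaching clear or almost clear skin with at least a two-grade improvement, and follow-up stops at Day 85. If fewer than half of an arm succeed, its median and 75th percentile do not exist. If fewer than a quarter succeed, the 25th does not exist either. The main rows of the table could then be blank in both arms, or filled in one arm only, and nothing in the table would measure the difference between arms or its uncertainty.

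The endpoint deserves a better summary because of the entry criteria. Subjects must have an IGA of 3 (Protocol 4.1), so for an eligible subject a score of 0 or 1 and a two-grade improvement are the same event. The other two IGA secondary endpoints in the SAP therefore repeat the primary endpoint. Time to success is the only IGA secondary endpoint that can add information.

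**Working it through.** The plan states no power, event count, hazard ratio or success rate for this endpoint, so there is no figure to reproduce. The check asks which percentiles would exist, and what a formal comparison could offer at the same rates.

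**Inputs**
- 100 subjects per arm, 1:1 (SAP section 7).
- Post-baseline IGA at Days 15, 29, 57 and 85 (Protocol 6.1).
- Cumulative first-success rate: not in the documents. Assumed range 10% to 75%. The range includes 18.2% and 34.8%, the only earlier response rates given (Protocol 1.3.2). Those are for a different endpoint, a Signs of AD improvement at 4 weeks, and serve only as markers.
- Dropout: no rate given. Assumed 0% and 15%.
- Two-sided 0.05, assumed for illustration.

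**Step 1. Does a percentile exist?** The 25th, 50th and 75th percentiles need the curve to fall to 0.75, 0.50 and 0.25. Without dropout, that means at least 25, 50 or 75 first successes among 100. The probability is P(X ≥ k) with X ~ Binomial(100, p).

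| Cumulative success p | 25th reached | 50th reached | 75th reached |
|---|---|---|---|
| 10% | 0.00 | 0.00 | 0.00 |
| 18.2% | 0.055 | 0.00 | 0.00 |
| 20% | 0.13 | 0.00 | 0.00 |
| 25% | 0.54 | 0.00 | 0.00 |
| 30% | 0.89 | 0.00 | 0.00 |
| 34.8% | 0.99 | 0.001 | 0.00 |
| 40% | 1.00 | 0.03 | 0.00 |
| 45% | 1.00 | 0.18 | 0.00 |
| 50% | 1.00 | 0.54 | 0.00 |
| 60% | 1.00 | 0.98 | 0.001 |
| 75% | 1.00 | 1.00 | 0.55 |

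If the curve must fall strictly below the level (26, 51 or 76 events), the values are a little lower: 0.087 for the 25th at 20%, and 0.46 for the median at 50%. A simulation on the four visits (4,000 runs, events assumed split 10/20/35/35% over the visits) with 15% dropout gives 0.50 for the 25th percentile at 25%, 0.98 at 34.8%, and 0.18 for the median at 45%.

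**Step 2. What could a comparison show?** With proportional hazards and no dropout:
- HR = ln(1 − p_active) / ln(1 − p_vehicle)
- events d = 100 × (p_vehicle + p_active)
- power = Φ(√d × ln HR / 2 − 1.96) (Schoenfeld)

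For 15% versus 30%: HR = ln 0.70 / ln 0.85 = 2.19; d = 45; √45 × 0.786 / 2 − 1.96 = 0.68; power = 75%. The simulated log-rank test gives 71%.

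| Vehicle vs active | Mean number of 6 percentiles reached | 25th reached in both arms | HR | Events | Log-rank power, Schoenfeld / simulated |
|---|---|---|---|---|---|
| 10% vs 20% | 0.13 | 0.00 | 2.12 | 30 | 54% / 51% |
| 10% vs 25% | 0.54 | 0.00 | 2.73 | 35 | 84% / 81% |
| 15% vs 30% | 0.89 | 0.005 | 2.19 | 45 | 75% / 71% |
| 18.2% vs 34.8% | 1.04 | 0.05 | 2.13 | 53 | 79% / 76% |
| 25% vs 40% | 1.56 | 0.53 | 1.78 | 65 | 64% / 63% |

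**Step 3. What would cumulative success with an interval show?** Without dropout the Kaplan-Meier variance equals the binomial one. At 30%, the half-width is 1.96 × √(0.30 × 0.70 / 100) = 9.0 points. At 15%, it is 1.96 × √(0.15 × 0.85 / 100) = 7.0 points. For the 15-point difference, it is 1.96 × √(0.0021 + 0.001275) = 11.4 points. These estimates exist whatever the rates are.

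**The case against.** A reader might infer that the endpoint is reported by quartiles alone and permits no comparison at all. The documents do not support that. Curves by arm are planned in three populations, and the table carries success and censored counts. A descriptive comparison is possible even if every percentile is unreached; what is missing is a formal one.

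A reader might also infer that onset of effect goes untested. That is too strong. SAP 6.9.1.3 applies the primary logistic regression to IGA success at Days 15, 29 and 57, with a p-value at each visit. The repeated-measures model in SAP 6.10.1 includes a treatment-by-visit term. With only four post-baseline assessments, these supply much of the onset information. They are proportions in success at a given visit, however. The first set rests on LOCF, and neither estimates cumulative first success with censoring taken into account.

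Nor is descriptive reporting a departure from the protocol. Protocol 9.2 disclaims hypothesis testing, and I-NRS, another secondary endpoint, is also only summarised. On the other side, Protocol 9.3.7 and SAP 6.1.8 allow unadjusted exploratory tests, and the SAP attaches a p-value to every other secondary endpoint it lists. An addition is therefore compatible with the plan, though not required by it.

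Last, the success rates are assumed. First success at any visit can exceed the Day 85 rate, and from about 60% cumulative success two of the three percentiles per arm would be reached. This stands, and the conclusion has to be conditional on the rate.

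**Conclusion.** The point holds as a matter of informativeness, and it is minor. This secondary endpoint has no effect estimate, confidence interval or formal between-arm comparison; that follows from the text and needs no assumption. How empty the percentile rows will be does depend on one. Below about 45–50% cumulative first success, at most one of three percentiles per arm is likely to be estimable. At 20% or below, usually none is. Two of three become likely only above about 50%.

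Across the assumed pairs, on average 0.1 to 1.6 of the six percentiles would be available, where a log-rank test would have roughly 51% to 84% power. Those power figures assume 100 per arm, proportional hazards and no dropout. They should not be ranked against the power of the Day 85 proportion, because cumulative first success and success at Day 85 are different quantities.

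The documents do not support saying that most percentiles will be unreached, only that they may be. The primary analysis is unaffected.

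**What to change.** In SAP 6.8.2.5 and Table 14.2.2.4.1:

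1. Add Kaplan-Meier cumulative success by arm, with 95% confidence intervals, at Days 15, 29, 57 and 85. Use the nominal visit as the time scale: the Day 85 visit may fall up to five days late, and a curve read at calendar Day 85 would miss those successes.
2. Add an exploratory log-rank test and a hazard ratio with 95% confidence interval. Because IGA is assessed at only four post-baseline visits, event times are grouped and heavily tied. Take the hazard ratio from a discrete-time model (for example, complementary log-log), or name the tie handling for a Cox model.
3. Keep the three percentiles and state that unreached ones are shown as not estimable.
4. Label the test exploratory and unadjusted, in line with SAP 6.1.8. If the sponsor prefers to follow Protocol 9.2 strictly, item 1 can stand without item 2.

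The cost is a few lines of text and some extra table rows, with no new data. The downside is one more unadjusted exploratory comparison.

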6.3.7. Day 85 Visit/End of Study Visit

The final application of study drug will occur on the evening prior to the Day 85 Visit. If the Day 85 visit is delayed, the subject should continue BID application until the evening before the Day 85 Visit. At the Day 85 Visit (Day 85 \pm 5 days), the following will be conducted:

- Collect and weigh returned study drug pumps
- Collect study diary
- Query subject for adverse events that occurred since the previous visit
- Query subject for changes in concomitant medications
- Collect blood sample for CBC and chemistry
- Collect urine sample for urinalysis
- Conduct UPT (WOCBP only)
- Perform IGA
- Calculate BSA of total AD involvement
- Assess Signs of AD score
- Collect EASI score
- Collect I-NRS
- Photographs and Signs of AD scoring of target lesion (selected sites only)
- Discharge subject from study

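### Time to IGA success: Day 85 failures are censored on the day seen, so the Kaplan-Meier curve overstates success when final visits are spread across the ±5-day window

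*SAP*

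**What the plan says.** SAP 6.8.2.5 covers a named secondary endpoint: "Time to achieve IGA success will be summarized using the Kaplan-Meier method and displayed graphically". It adds "Medians, as well as 25% and 75% percentiles will be presented". Two rules set the times:

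- Events: "Elapsed times will be computed from the date of first dose to the date of IGA assessment".
- Non-events: "Subjects not achieving the event by the time of completion/discontinuation will be right censored using the date of the last recorded non-missing assessment".

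The shell of Table 14.2.2.4.1 repeats the first rule in its footnote and marks the three percentiles as "Estimated using Kaplan-Meier methods". The table is repeated for the mITT and PP populations, and a Kaplan-Meier figure is planned for each of the three populations.

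The protocol (6.3 and Table 4) schedules post-Baseline IGA at Days 15 and 29 (each ±3 days) and Days 57 and 85 (each ±5 days). Subjects are discharged at the Day 85 visit, so no IGA follows it.

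SAP 6.1.3 summarises scheduled data by nominal visit, but 6.8.2.5 and the table footnote specify actual dates for this endpoint.

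**The concern.** IGA status is known only at four visits. For a completer, the Day 85 visit settles whether success was reached by the end of the study, whichever calendar day it took place. Under the date rule, a completer who fails is censored on that calendar day. Kaplan-Meier then treats the subject as having unknown status from that day on and passes the subject's weight to those who attend later in the window. Attending on Day 83 rather than Day 88 is a matter of scheduling, so the redistribution has no justification.

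The earlier visits do not share the problem. A subject without success at Day 15, 29 or 57 normally stays at risk until a later visit, and the visit windows do not overlap.

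At stake are the right-hand end of the curve and the quartiles. The error runs one way: interleaved censoring can only shrink the risk set, so cumulative success is overstated or unchanged. The plan can therefore print a 25th percentile, and sometimes a median, that the observed successes do not support. Neither the table nor the SAP text provides numbers at risk or confidence intervals that would warn the reader.

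**Working it through.** The plan states no success rate, event count or expected curve, so there is no figure of its own to reproduce.

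**Inputs from the documents.** 100 subjects per arm (SAP 7); final visit Day 85 ±5, that is 11 calendar days, with no later follow-up (Protocol 6.3.7); dates and Kaplan-Meier as above (SAP 6.8.2.5).

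**Assumed, because the documents are silent.** True success by Day 85 of 10%, 20% or 30%; 35% of successes first seen at Day 85; visit dates uniform over the window, or with an SD of 2 days or 1 day; no dropout.

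**Step 1: size of the distortion.** Let *p* be the success probability at the final visit among subjects still at risk, with visits uniform over 11 days. When *k* days of the window remain, the risk set is *k*/11 of those subjects and that day's successes are *p*/11, so the step is *p*/*k*. The final visit then adds about 1 − ∏(1 − *p*/*k*), *k* = 1 to 11, where it should add *p*:

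| *p* | Date-based addition |
|---|---|
| 5% | 14% |
| 10% | 27% |
| 15% | 38% |
| 20% | 47% |

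For small *p* the multiplier approaches 1 + 1/2 + … + 1/11 = 3.02.

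**Step 2: worked example.** Take 100 subjects, no dropout, and 2, 4, 7 and 7 successes at the four visits: 20 in all. After Day 57, 13 have succeeded and 87 remain. They attend the last visit on seven successive days.

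| Day in window | Attend | At risk | Successes | Kaplan-Meier success |
|---|---|---|---|---|
| 1 | 4 | 87 | 0 | 13.0% |
| 2 | 10 | 83 | 1 | 14.0% |
| 3 | 16 | 73 | 1 | 15.2% |
| 4 | 27 | 57 | 2 | 18.2% |
| 5 | 16 | 30 | 1 | 20.9% |
| 6 | 10 | 14 | 1 | 26.6% |
| 7 | 4 | 4 | 1 | 44.9% |

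On nominal days the same data give 1 − 0.87 × (80/87) = 20.0%, with no 25th percentile. On actual dates the curve ends at 44.9% and a 25th percentile is printed. This example is unfavourable: the expected number of successes among the last four attenders is 4 × 7/87 = 0.32, and here there is one. Step 3 gives averages.

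**Step 3: simulation.** 100 per arm, with the SAP rule applied to simulated visit dates. Ranges cover the three visit spreads.

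| True success | Mean end of curve, actual dates | Mean, nominal days | 25th percentile printed although <25% succeeded (share of arms) |
|---|---|---|---|
| 10% | about 17-20% | 10.0-10.1% | about 13-18% |
| 20% | about 32-35% | 19.9-20.0% | about 50-63% |
| 30% | about 46-51% | 30.0-30.2% | not tabulated |

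The curve reaches 100% in about 0-7% of arms across these scenarios; this needs the last attender or attenders all to be successes. In separate runs, 15% dropout left the results about the same, and with every visit exactly on target the two versions coincided.

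**The case against.** The strongest reply is that little depends on this curve. SAP 6.8.2.5 plans no log-rank test, hazard ratio or p-value; all tests in the study are exploratory; and the primary analysis is a separate logistic regression at Day 85. Table 14.2.2.4.1 also prints the crude number and percentage of subjects with IGA success directly above the quartiles, the figures mark censored observations, and IGA success by visit is tabulated elsewhere. All of this stands. It limits the consequence but does not correct the estimate: for a descriptive endpoint the curve and its quartiles are the result.

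A second reply is that SAP 6.1.3 already uses nominal visits. That does not rescue the endpoint, because 6.8.2.5 and the table footnote explicitly prescribe dates, and a programmer following them reproduces the error.

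A third reply is that the size is conjecture. That is fair in part. It depends on success rates and visit spread that the documents do not give, and it is zero when visits fall on target. The direction does not depend on those assumptions.

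**Conclusion.** As written, the rule overstates cumulative IGA success whenever final visits are spread over the window and some successes occur after failures have been censored. Under the stated assumptions the end of the curve is about 1.5 to 2 times the true proportion (for example 32-35% against 20%), and at 20% true success an unsupported 25th percentile appears in about half to three-fifths of arms. These rates are per arm, not per trial.

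Three stronger readings should be resisted:

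- A reader might infer that the curve is always wrong. It is not: with on-target visits the error is nil, and the documents do not say how visits will be spread.
- A reader might infer that the true proportion is hidden or that the efficacy conclusion is compromised. The crude proportion stands in the same table, no between-arm test uses these times, and the primary analysis is untouched.
- A reader might infer that curves running to 100% are to be expected. Under these assumptions they occur in about 0-7% of arms.

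The rule should be corrected before analysis because it is wrong and cheap to fix, but it does not threaten the trial's main result.

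**What to change.** In SAP 6.8.2.5, the footnote of Table 14.2.2.4.1, its mITT and PP repeats and the three figures, set event and censoring times to the nominal visit day (15, 29, 57 or 85), with events taken before censorings at ties. Day 85 successes are then counted against everyone assessed at that visit.

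The off-schedule assessments need an explicit rule. SAP 6.1.3 excludes early-termination and unscheduled data before study day 9, and also excludes such data when the mapped visit already has a scheduled value. Applied unchanged, it would lose a first success at an unscheduled Day 40 visit that follows a scheduled Day 29 visit. State that, for this endpoint:

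- unscheduled and early-termination IGA assessments take the nominal day of their analysis window even when a scheduled value exists;
- subjects whose only post-Baseline IGA is before Day 9 are censored at that day.

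Do not offer a Turnbull (interval-censored) estimator on actual dates as an alternative, because it keeps much of the bias. On the worked example, with the seven days taken as Days 82 to 88, it ends at 34.75% and still prints a 25th percentile. In simulation at 20% true success it averages 25-30%, with an unsupported 25th percentile in 28-34% of arms.

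The cost is a few sentences, one footnote and a small programming change. Times will take essentially four values, but IGA is scheduled at only four post-Baseline visits, so little real resolution is lost.
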